2.2.4. CURRENT EVIDENCE ON THE USE OF TRANEXAMIC ACID IN PREVENTING PPH

In a randomized controlled trial (RCT) by Sujata and colleagues in 2016 of TXA among 60 parturients at increased risk of PPH undergoing elective or emergency caesarean delivery at a tertiary centre in India from August 2012 to April 2013, intravenous TXA 10mg/kg administered 10 minutes before skin incision significantly reduced the requirement for additional uterotronics within 24 hours (the primary outcome). Additional uterotronics were required in 23% of the patients assigned to TXA compared to 83% of patients given placebo ($P<0.001$). The trial, however, was small with only 60 participants, and anaesthetists were not blinded even though the patients and obstetricians were blinded to the interventions⁽⁴¹⁾.

A Cochrane database review by Sentilhes et. al. in 2015 found 10 RCTs evaluating the use of TXA in preventing PPH after caesarean birth. In all except one, caesareans were elective. The 10 RCTs all reported that women who received TXA had significantly less blood loss without any change in blood pressure, pulse and respiratory rate, or thrombosis. However, all the studies had several limitations that included being single-centre trials, not having a placebo in three, eight not clearly stating the primary outcome, and some quasi-randomized ⁽¹⁾.

The two most reliable studies in the review are summarized.

1. The first large double-blind RCT was reported by Gungorduk and colleagues in Turkey. The trial had an intention-to-treat analysis that included 660 women. This study had the most robust methodology. The primary outcome, estimated blood loss (EBL), was calculated by comparing the difference in haematocrits prior to and 48 hours after caesarean section. The reduction in bleeding at caesarean delivery attributed to TXA was significant [mean 499.9 (SD 206.4) ml vs 600.7 (215.7), P=0.001]. It also reduced the percentage of patients with blood loss more than 1000 ml [2.1% vs 5.8%; RR 2.7] (95% CI 1.1–6.3), P=0.03], and the requirement for supplementary uterotronics [8.5% vs 14.5%; RR 1.7 (95% CI 1.1–2.6), P=0.02]. The study enrolled 88% of eligible patients and had no patients lost to follow-up. The findings suggest TXA may be beneficial in decreasing blood loss after caesarean delivery and haemorrhage ^(1, 38).

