2.4. RESEARCH OBJECTIVES

1. To determine the effect of TXA (10mg/kg) given intravenously 10 minutes prior to an elective caesarean section on postpartum blood loss.
2. To determine the potential adverse effects of intravenous TXA given 10 minutes prior to elective caesarean section.

CHAPTER 3. RESEARCH METHODS

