1.11. STATISTICAL METHODS

Data analysis was conducted using Stata v15 (Stata Statistical Software: Release 15. College Station, TX: StataCorp LLC) following the CONSORT guidelines for reporting RCTs⁽⁵⁵⁾.

The primary analysis compared women given a low dose of TXA (10mg/kg) administered 10 minutes before elective caesarean section with prophylactic oxytocin administration to those given prophylactic oxytocin alone.

Baseline characteristics were compared between the groups to check the adequacy of randomization. Differences between patients lost to follow-up and included patients were also assessed. The intention-to-treat analysis was followed. This is a statistical concept whereby every participant in the study is accounted for in the analysis according to the randomization treatment assignment regardless of whether there is noncompliance, protocol deviations, withdrawal from the study, and anything happens after randomization⁽⁵⁶⁾.

Categorical data were reported using frequencies and proportions while continuous data were summarized using means and standard deviations for normally distributed data, and medians and quartile range where data was not normally distributed. Comparisons for categorical data were done using the chi-square test or Fisher's exact test when the sample size was small.

For continuous data, the t-test was used to compare differences between the groups and the analysis of variance (ANOVA) was used for comparing more than two groups. Where data were not normally distributed, the nonparametric Kruskal Wallis test was used to compare differences in continuous outcome for more than two groups. The Mann-Whitney U test was used to compare two groups where data were not normally distributed. Effect estimates were presented with relative risk measures and associated 95% confidence intervals. Any subgroup analysis was conducted as the primary analysis.

An analysis was conducted after 506 participants had been recruited to check if there are any significant differences in adverse events in the two groups.

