1.14. OUTCOMES

1.14.1. Primary Outcome

1. Incidence of PPH defined by blood loss equal to or exceeding 1,000 ml following elective caesarean section

- Based on calculated estimates.

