1.14.2. Secondary Outcomes

1. Incidence of PPH defined by blood loss equal to or exceeding 1000 ml following elective caesarean section

- Based on visual estimation

2. Estimated blood loss during caesarean section

- Based on visual estimate of blood loss and calculated estimates

3. Need for blood transfusion

- Mean or median number of units of red blood cells transfused up to day 2 postpartum

4. Use of additional uterotonicics (such as oxytocin infusion or prostaglandins)

- Number of participants who required additional uterotronics

5. Incidence of emergency surgical interventions for PPH up to day 2 post-surgery

6. Mean change in HCT up to day 2 post-surgery

- Difference between the HCT on the day before surgery and day 2 post-surgery

7. Mean peripartum change in haemoglobin up to day 2 post-surgery

- Difference between the haemoglobin on the day before surgery and at day 2 post-delivery

8. Duration of mother's hospital stay

9. TXA side effects

- number of participants with headache, anaphylaxis, nausea, diarrhoea, dizziness, fatigue, nasal sinus complaints, transient visual disturbances, abdominal pain, complaints of feeling faint, reported by anaesthetists and theatre staff [time frame: up to discharge from the recovery ward on day of surgery]
- number of participants with deep venous thrombosis, pulmonary embolism, myocardial infarction, or any thrombotic event confirmed by laboratory investigations up to day 2 post-surgery
- number of participants with seizures up to day 2 post-surgery
- number of participants with renal failure (defined by the need for dialysis) up to day 2 post-surgery
- number of participants with hypotension reported by anaesthetists and theatre staff [time frame: up to discharge from the recovery ward on day of surgery]
- Vital signs before surgery
 - Heart rate before surgery
 - Systolic BP before surgery
 - Diastolic BP before surgery

- Vital signs after placental delivery
 - Heart rate after delivery of the placenta
 - Systolic BP after delivery of the placenta
 - Diastolic BP after delivery of the placenta
- Post-caesarean delivery creatinine (mg/dL)
- Postoperative urea g/L
- Postoperative aspartate transaminase (IU/L)
- Postoperative alanine transaminase (IU/L)
- Postoperative total bilirubin (IU/L)

10. Neonatal outcomes

- Birth weight in grams determined on the date of delivery
- Apgar scores at 1 and 5 minutes on the date of delivery

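### For blood loss in ml, haematocrit change and haemoglobin change, the plan specifies no between-group difference with a confidence interval, and the quantity reported depends on an undefined normality check.

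*Combined protocol and SAP*

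**What the plan says.** The first objective in Section 2.4 is "To determine the effect of TXA (10mg/kg) given intravenously 10 minutes prior to an elective caesarean section on postpartum blood loss". Two kinds of outcome serve it. The primary outcome (Section 1.14.1) is binary: "Incidence of PPH defined by blood loss equal to or exceeding 1,000 ml following elective caesarean section", using calculated loss. Secondary outcome 2 (Section 1.14.2) is the amount of blood lost, "Based on visual estimate of blood loss and calculated estimates". Outcomes 6 and 7 are worded as means; outcome 6 reads "Mean change in HCT up to day 2 post-surgery", and outcome 7 is the matching change in haemoglobin.

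Section 1.11 sets the analysis. For data judged normal, "For continuous data, the t-test was used to compare differences between the groups", with means and SDs as summaries. Otherwise, medians and quartiles are given and "The Mann-Whitney U test was used to compare two groups where data were not normally distributed". Its only sentence on effect measures is "Effect estimates were presented with relative risk measures and associated 95% confidence intervals".

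Section 1.10 gives two formulas for calculated loss. One uses the haematocrit fall divided by the preoperative value. The other, added because haematocrit was not always available, uses the haemoglobin fall divided by the end value.

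**The concern.** A test of whether two groups differ does not say by how much. A Mann-Whitney p-value is unchanged by any increasing transformation of the data, so it holds no information in ml. Two group medians allow a reader to subtract, but give no interval for the difference. On the t-test branch a mean difference could be derived, but the plan does not say that it will be reported or given an interval.

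The switch also leaves the target open. No test, threshold or graphical rule for normality is stated, so whether the trial reports a mean or a median is settled after the data are seen. For outcomes 6 and 7 this can contradict the outcome definition itself. For blood loss, the upper tail is the clinically interesting part, and a median or rank summary gives it less weight than a mean does. Section 2.2.4 summarises blood loss in earlier trials by means, so a median with a p-value would also be hard to set beside them.

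**Working it through.** **1. The plan's own figure.** Section 1.4 assumes PPH of 2.1% and 5.8%, two-sided alpha 0.05, 90% power and equal groups. The Fleiss formula without continuity correction gives 581 per group (579.8 with the printed z values 1.96 and 1.28). The stated 581 reproduces. It concerns the binary outcome only and is not in dispute.

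**2. Inputs for blood loss in ml.** From the planning trial in Section 2.2.4: "mean 499.9 (SD 206.4) ml vs 600.7 (215.7), P=0.001", TXA first. The difference is 600.7 − 499.9 = 100.8 ml. Group sizes are 581 (planned) and 253 (half of the 506 recruited in the initial period, Section 1.6, assuming an equal split).

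**3. Precision of a difference in means.** Half-width = 1.96 × √(s₁²/n + s₂²/n), where s₁² + s₂² = 206.4² + 215.7² = 89,127.

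| n per arm | SE (ml) | 95% half-width (ml) | Interval around 100.8 ml |
|---|---|---|---|
| 581 | √(89,127/581) = 12.39 | 24.3 | about 77 to 125 |
| 253 | √(89,127/253) = 18.77 | 36.8 | about 64 to 138 |

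**4. Is skew plausible?** If loss were normal, the share above 1,000 ml would be:
- TXA: (1000 − 499.9)/206.4 = 2.42, so 0.8%, against 2.1% reported.
- Control: (1000 − 600.7)/215.7 = 1.85, so 3.2%, against 5.8% reported.

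A gamma distribution with the same means and SDs gives 2.1% and 4.8%, which is closer. Right skew is therefore plausible.

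**5. Would the rank branch be taken?** The plan names no normality test, so Shapiro-Wilk at 5% is an illustration. For pure gamma data with the control mean and SD it rejects in about 99% of samples of 253 and 100% of samples of 581. However, calculated loss is built from a before-and-after difference, which can be negative and carries measurement and fluid noise. If 30% of the variance is symmetric noise, rejection at 253 falls to about 50%; with 50% noise it falls to about 20%. At 581 the figures are about 87% and 31%. The noise shares are assumptions.

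**6. Does skew invalidate the mean?** With lognormal losses having the means and SDs above, the Welch 95% interval covered the true difference in 95.1% of simulated trials at 581 per arm and 94.8% at 253.

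**7. Rank-based alternative.** In the same simulations the Hodges-Lehmann shift was about 100 ml, with half-widths of about 22 ml (581) and 33 ml (253). For a 40 ml difference under lognormal skew at 253 per arm, Mann-Whitney had about 62% power and Welch about 55%.

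**The case against.** The strongest reply is that little is lost. The sentence on relative risk does not forbid other estimates, the t-test branch compares means, and the skewed branch still shows medians and quartiles in ml. A reader might infer that no effect size in ml will ever appear; the text supports only that none is specified with an interval.

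A reader might also infer that objective 1 has no estimate at all. It has one: relative risk with a 95% interval is a proper measure for the primary outcome and answers the research question in Section 1.4 of the introduction, which is about PPH incidence.

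Two further inferences go too far. One is that the rank branch is nearly certain to be used: step 5 shows that this depends on an unnamed test and on how noisy calculated loss is, and the documents give no evidence of skew in haematocrit or haemoglobin change. The other is that the mean difference is the most precise answer available: step 7 shows a rank-based shift slightly tighter under skew. Power for 100.8 ml at 253 per arm exceeds 99.9% against 57% for binary PPH, but that compares two outcomes, not two tests.

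These points limit the reach of the concern. None of them supplies the missing estimate, and the general commitment to CONSORT reporting names no measure for continuous outcomes.

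**Conclusion.** The point holds for the continuous secondary outcomes: blood loss by visual and calculated methods, haematocrit change and haemoglobin change. Followed as written, Section 1.11 yields no pre-stated between-group difference with an interval, and it leaves the choice of mean or median to an undefined look at the data. The conflict with outcomes 6 and 7 is conditional: it arises only if those variables are judged non-normal. The binary primary outcome and the sample size are untouched.

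The change should be made but is not critical. What it would add is an interval of about ±24 ml at 581 per arm or ±37 ml at 253, valid under the skew examined. These figures assume the planning trial's SDs, an equal split of the 506 and no missing values; the lognormal and gamma shapes are illustrative.

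**What to change.** In Section 1.11, for visual and calculated blood loss, haematocrit change and haemoglobin change:

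- Report the difference in means (TXA minus control) with a 95% Welch confidence interval, whatever the distribution, and a bootstrap interval as a check.
- Keep Mann-Whitney as a supporting test, with a Hodges-Lehmann shift and interval if wanted. It need not be dropped.
- State which calculated loss in Section 1.10, the haematocrit or the haemoglobin formula, is the main one, and report the other as a sensitivity analysis. Without this the quantity is still not fixed.
- As a small addition for PPH, give the risk difference with its 95% interval beside the relative risk (2.1% − 5.8% = −3.7 percentage points under the planning rates).
- Label the change as post hoc for any data already analysed at 506 participants.

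The cost is wording and a few lines of Stata, with no new data and no change to the sample size. The downside is small: a mean is more sensitive to a few extreme values, which the bootstrap helps to check, and under skew it can be slightly less powerful than the rank test, which stays as support.

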1.4. SAMPLE SIZE

The sample size was calculated assuming a proportion of 2.1% PPH in the experimental group and 5.8% in the control group ⁽³⁸⁾ at 95% confidence interval and 90% power using the Fleiss formula giving a minimum sample size of

$$\begin{aligned} n &= \frac{[Z_{\alpha/2}\sqrt{(r+1)\bar{p}\bar{q}} + Z_{\beta}\sqrt{rp_1q_1 + p_2q_2}]^2}{r(p_1 - p_2)^2} \\ &= \frac{[1.96\sqrt{(1+1) \times 0.0395 \times 0.9605} + 1.28\sqrt{0.021 \times 0.979 + 0.058 \times 0.942}]^2}{(0.021 - 0.058)^2} \\ &= 581 \text{ per group} \end{aligned}$$

Thus, total minimum sample size $N = 1,162$ women

Where: n = sample size

$Z\alpha = 1.96$ at 95% confidence interval

$\alpha = \text{probability of a type I error (significance level)} = 0.05$

$\beta = \text{probability of a type II error (1 - power of test)}$

$p_1 = \text{proportion of PPH in the experimental group} = 0.021$

$p_2 = \text{proportion of PPH in the control group} = 0.058$

$r = \text{ratio of control group/population 2 to experimental group/population 1}$

$q = 1-p$

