1.6. RANDOMIZATION

A randomized allocation to study and control groups using computer-generated random numbers was done by the trial statistician.

Equal numbers were randomly allocated to the two groups for the two hospitals.

Based on the sample size the plan was for the statistician to prepare random numbers for 1,162 patients. Half of these numbers were labelled with A which represented the intervention 10mg/kg TXA and oxytocin 5IU e.g. random number 4A, represented random number 4, allocated to group A. The other half had the extension B (control group) to receive Oxytocin 5IU only.

The computer-generated numbers assigned the trial group and also a unique participant number. The numbered folded slips of paper were placed into sealed identical envelopes by the principal investigator. The sealed envelopes were kept in a box at each hospital in a locked-up room. At the beginning of the trial, TXA for 200 patients was available. The statistician therefore initially prepared random numbers for 400 patients (200 with the extension A and 200 with the extension B), half of which were prepared for HMH (1 – 200) and the other half for MNMH (1 – 200). A further 106 were prepared when the 400 numbers were used up to make the total number recruited 506 during the initial trial period.

The patients were enrolled by the principal investigator or the research assistants on the day before their scheduled caesarean section. Once they met the study criteria per the screening tool (see **Error!**

Reference source not found.), informed consent was obtained (**Error! Reference source not found.** & **Error! Reference source not found.**). The participant was asked to pick an envelope from the box. The envelope would then be opened by either the participant or the researcher.

The study number would then be entered on the data collection tool as the study serial number. A unique study sticker labelled 'Group A' / 'TXA' or 'Control' would be attached to the patient's notes. The data tool would then be inserted into the notes together with a prescription form if in group A for the attention of the theatre staff and anaesthetists. (Refer to **Error! Reference source not found.**). Only the data tool was attached to the control group patient's notes. (**Error! Reference source not found.**). A list matching the serial number to the allocated group was compiled to match the original randomization.

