The calculated method and visual estimation of blood loss were used in this study. Although visual estimation is the method used frequently by anaesthetists to estimate blood loss, it has been demonstrated as inaccurate in repeated studies. Its continued use in clinical practice is related to tradition and ease of use. This method was compared with the calculated method by Stafford et. al. who noted that these calculations could be inaccurate based on the hydration status of women, particularly related to intravenous loading conducted during regional anaesthesia (>90% had an epidural), or with pregnancy-induced hypertension. They also acknowledged that maternal physiologic changes may alter the haematocrit changes. Plasma volume increases by on average 1.25 litres in all pregnant women, and all will undergo fluid changes post-delivery^(23, 53, 54). In addition, all of the participants received intravenous fluids as they are surgical patients. Therefore, any effects on the haematocrit of the physiological changes or IV fluids happened in all the participants as the plasma volume changes were universal to all pregnant women. Secondly, we intended to do a subgroup analysis of women who had pregnancy-induced-hypertension. Women with Eclampsia/HELLP syndrome were excluded from the study. As visual estimation is the method traditionally used at both hospitals, we used this together with the more objective calculated method for comparison to determine blood loss.

Refer to **Error! Reference source not found.** for the patient flow in the study.

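### Subgroups are analysed by repeating the primary test, with no test of whether the TXA effect differs between them, so a non-significant result in women with pregnancy-induced hypertension would be uninformative

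*Combined protocol and SAP*

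**What the plan says.** Section 1.11 (Statistical Methods) defines the primary analysis as TXA plus oxytocin against oxytocin alone. Categorical outcomes are compared by chi-square, or by Fisher's exact test when numbers are small, and effects are given as relative risks with 95% confidence intervals. On subgroups it says only: "Any subgroup analysis was conducted as the primary analysis". It sets no limit on the number of subgroups, and the document contains no interaction test, no multiplicity rule for subgroups and no exploratory label.

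Section 1.10 (Assessment) names one subgroup: "we intended to do a subgroup analysis of women who had pregnancy-induced-hypertension". It does so while answering a worry that the haematocrit-based calculation of blood loss may be inaccurate in some women, including those with PIH. That calculation defines the primary outcome in section 1.14.1. The document does not give the PIH share, does not describe a comparison with women who do not have PIH, and does not say how a subgroup difference would be judged.

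**The concern.** A TXA-versus-control test within a subgroup asks whether an effect is detectable in those women. It does not ask whether the effect there differs from the effect in other women. Answering that needs a direct contrast between strata, and the plan has none.

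Two things are at stake. First, a small PIH subgroup is likely to be non-significant whatever the truth, so a null result there carries almost no information. Second, if the result in PIH women is set beside the result in the rest, one significant p-value and one non-significant p-value can look like a difference in effect when there is none.

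**Working it through.** **Inputs from the document**
- Design rates (section 1.4): "assuming a proportion of 2.1% PPH in the experimental group and 5.8% in the control group".
- Two-sided alpha 0.05 with z = 1.96, and "90% power using the Fleiss formula giving a minimum sample size of" 581 per group, or 1,162 in total (section 1.4).
- Recruitment so far (section 1.6): batches prepared "to make the total number recruited 506 during the initial trial period".
- Allocation (section 1.6): "Equal numbers were randomly allocated to the two groups for the two hospitals", so 581 or 253 per arm.

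**Assumptions, because the document is silent**
- PIH share: 15% as the base case, 5% to 50% as the range.
- Fisher's test is used when the pooled expected event count per arm is below 5. The plan gives no threshold, so chi-square results are shown too.
- The same 2.1% versus 5.8% holds in both strata, that is, a uniform effect.

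**Step 1. The plan's own figure.** With p̄ = 0.0395, n = [1.960·√(2 × 0.0395 × 0.9605) + 1.2816·√(0.021 × 0.979 + 0.058 × 0.942)]² / 0.037² = 580.3, which rounds up to 581. The stated sample size reproduces.

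**Step 2. Stratum sizes and expected events at a 15% share.** At 1,162 there are 87 PIH and 494 other women per arm. At 506 there are 38 and 215. Average expected PIH events per arm are 87 × 0.0395 = 3.4 and 38 × 0.0395 = 1.5, so Fisher's test would normally apply in the PIH stratum.

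**Step 3. Power and discordance.** Power is by exact binomial enumeration. The strata contain different women, so the tests are independent and P(exactly one significant) = a(1 − b) + b(1 − a), with a the power in PIH and b the power in the rest.

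| N | Test at small counts | PIH power | Power in the rest | Exactly one significant |
|---|---|---|---|---|
| 1,162 | Fisher | 12.4% | 86.4% | 77.4% |
| 1,162 | chi-square | 21.3% | 86.4% | 70.9% |
| 506 | Fisher | 1.0% | 51.4% | 51.4% |
| 506 | chi-square | 8.8% | 51.6% | 51.3% |

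First row as an example: 0.124 × 0.136 + 0.864 × 0.876 = 0.774.

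**Step 4. Sensitivity of discordance (Fisher rule).**
- PIH share 5%, 10%, 20%, 30%, 50% at 1,162: 90%, 85%, 69%, 55%, 46%. At 506: 56%, 54%, 49%, 44%, 39%.
- Weaker uniform effect, share 10% to 20%: 2.9% versus 5.8% gives 56% to 63% at 1,162 and 30% to 33% at 506; 3.5% versus 5.8% gives 41% to 43% and 20% to 21%.
- PIH control rate doubled to 11.6% with the same relative risk, at 1,162: 68%, 45% and 36% for shares of 10%, 20% and 30%.

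**Step 5. The alternative.** A Wald interaction test on the log relative risk, simulated under the same uniform effect with 0.5 added to each event count (200,000 replicates, shares 10% to 50%), falsely declares a difference in about 2% to 3% of trials at 1,162 and 1% to 2% at 506.

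**Step 6. Sparse cells.** With 38 PIH women on TXA, the chance of no event is 0.979³⁸ = 45%; with 87 it is 0.979⁸⁷ = 16%. With an empty cell, an ordinary log-binomial or Poisson interaction term has no finite estimate.

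**The case against.** The strongest reply is that section 1.10 mentions only an analysis of women with PIH. It does not say that women without PIH form a second tested stratum, or that one p-value will be read against the other. This stands: the discordance figures apply only if both are tested. The low PIH power does not depend on that reading.

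It is also fair that no subgroup result is listed among the outcomes, that only one subgroup is named, and that relative risks with confidence intervals are already planned. The primary conclusion is unaffected.

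A reader might infer three stronger points that the document does not support.
- **That a uniform effect will usually look different between women with and without PIH.** This needs the full design effect, the planned 1,162 women and a modest PIH share. At 506 it is about even odds or less, and a weaker effect lowers it further (Step 4).
- **That testing two strata nearly doubles the false-positive risk.** With 4% PPH in both arms and a 15% share, the chance of at least one significant stratum is 9.0% at 1,162 with chi-square throughout. Under the Fisher rule it is 6.5% at 1,162 and 5.1% at 506, so little inflation remains.
- **That an interaction test would settle whether calculated blood loss is valid in PIH.** It tests effect modification, not measurement error.

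**Conclusion.** The point holds as a defect of method. The stated rule cannot show whether the TXA effect differs between subgroups, and a non-significant PIH result would be uninformative: at an assumed 15% share and the full design effect, PIH power is 12% to 21% at 1,162 women and 1% to 9% at 506, depending on the test. If both strata are tested, a uniform effect gives exactly one significant stratum in about 71% to 77% of trials at 1,162 and about 51% at 506.

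These sizes rest on a PIH share that the document does not give, on equal rates across strata, and, for discordance, on an inferred comparison of women with and without PIH. The absence of a between-strata test rests on none of these. The matter should be corrected, but it does not touch the primary comparison.

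**What to change.** Replace the subgroup sentence in section 1.11 with:

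> Subgroup effects are assessed by a treatment-by-subgroup interaction test on PPH (modified Poisson, or an exact or penalised method if a cell has no events), with relative risks and 95% CIs by stratum. No claim is made from within-stratum p-values. PIH is the only planned subgroup, and all subgroup results are exploratory.

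Treat the validity of calculated blood loss in PIH as a separate question. Compare calculated with visual loss in women with and without PIH; both measures are already collected.

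The cost is one sentence, one extra model and one descriptive comparison, with no new data, so it can be done at analysis or reporting. The downside is that the interaction test has low power, so a non-significant interaction is not evidence that the effect is the same, and the result is descriptive.

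### For rare serious harms, a check for significant differences at 506 women, with relative risk as the only named effect estimate, cannot inform the safety objective

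*Combined protocol and SAP*

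**What the plan says.** All references are to the combined protocol and SAP.

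- Section 2.4 sets two objectives. The second is: "To determine the potential adverse effects of intravenous TXA given 10 minutes prior to elective caesarean section".
- Section 1.11 (Statistical methods) has one sentence specific to harms. It describes an analysis after 506 recruits "to check if there are any significant differences in adverse events in the two groups".
- The same section names one kind of between-group estimate: "Effect estimates were presented with relative risk measures and associated 95% confidence intervals". It also plans frequencies and proportions for categorical data, chi-square or Fisher's exact test for small samples, and separate summaries and tests for continuous data. It names no risk difference and gives no rule for an outcome with no events in an arm.
- Section 1.14.2 lists the harms. Some are likely to be rare: venous and arterial thrombosis (including "any thrombotic event confirmed by laboratory investigations up to day 2 post-surgery"), seizures, and renal failure needing dialysis. Others may be fairly common, such as nausea, headache, dizziness and hypotension. No expected rates are given for any of them.
- Section 1.4 contains the only power calculation. It is for postpartum haemorrhage, "at 95% confidence interval and 90% power using the Fleiss formula".
- Section 3.16 gives the monitoring board access to the safety data, and section 3.17 sets a stopping rule based on judgement, with no p-value.

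**The concern.** When events are rare, a significance check gives nearly the same answer whether or not the drug causes harm. The exclusions in section 1.2 (previous thrombosis, coagulopathy, epilepsy or seizures, renal disorders) and the two-day window make low counts of the serious events more likely still.

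Relative risk does not fill the gap. With no events in the control arm it is infinite, with none in the TXA arm it is zero, and with none in either it is undefined. The usual log-scale interval exists in none of these cases.

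What is at stake is the answer to objective 2. Section 2.3 presents TXA as simple to add to routine care. If the report gave only the result of the check and a relative risk for thrombosis or seizures, a reader could not tell how large an excess the data leave open.

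**Working it through.** **Inputs.** 506 women come from section 1.6: "A further 106 were prepared when the 400 numbers were used up to make the total number recruited 506". Allocation is 1:1 ("Equal numbers were randomly allocated to the two groups for the two hospitals"), but the split of the last 106 is not stated, so 506 / 2 = 253 per arm is an assumption. Two-sided alpha is 0.05 (section 1.4, Z = 1.96). The full planned size is 581 per arm. Every harm rate below is an assumption, shown as a range.

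**1. The plan's own figure.** With p1 = 0.021, p2 = 0.058 and mean (0.021 + 0.058)/2 = 0.0395:

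n = [1.96·√(2 × 0.0395 × 0.9605) + 1.28·√(0.021 × 0.979 + 0.058 × 0.942)]² / 0.037² = 579.8

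Unrounded z values give 581 after rounding up, so 581 per group (1,162 in total) is reproduced. It concerns haemorrhage only.

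**2. Power for harms.** Power is the sum, over all count pairs (x, y), of Bin(x; n, control rate) × Bin(y; n, TXA rate) for pairs with two-sided Fisher p<0.05. Fisher is the plan's small-sample option.

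| Assumed control vs TXA rate | 253 per arm | 581 per arm |
|---|---|---|
| 0.5% vs 1% | 1.4% | 8.6% |
| 1% vs 2% | 6.9% | 21% |
| 1% vs 3% | 24% | 63% |
| 5% vs 10% | 52% | 89% |
| 10% vs 20% | 87% | 99.8% |

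Uncorrected chi-square is somewhat more favourable at 253 per arm (7.9%, 13.6% and 35.5% for the first three rows) but leads to the same conclusion. By the plan's type of formula, 80% power for the first two rows would need about 4,673 and 2,319 per arm.

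**3. Smallest significant split against a zero arm.** At 253 per arm, 5 vs 0 gives p = 0.061 and 6 vs 0 gives p = 0.030. At 581 per arm the values are 0.062 and 0.031. Six events against none are needed at either size.

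**4. Chance that at least one arm has no events, 253 per arm.** This is 1 − [1 − (1 − pc)^253]·[1 − (1 − pt)^253], where pc and pt are the control and TXA rates.

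- 0.1% vs 0.2%: zero-event chances 0.776 and 0.603, so 1 − 0.224 × 0.397 = 91%. Both arms are empty with chance 0.776 × 0.603 = 47%.
- 0.5% vs 1%: 0.281 and 0.079, so 1 − 0.719 × 0.921 = 34%.
- 1% vs 2%: 0.079 and 0.006, so 8%.

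**5. What can still be said with zero events.** The exact upper limit is 1 − 0.025^(1/n) (two-sided 95%) or 1 − 0.05^(1/n) (one-sided 95%). For 0/253 this is 1.4% or 1.2%. For 0/581 it is 0.63% or 0.51%.

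**6. What a risk difference would show.** Newcombe (score-based) 95% intervals, TXA minus control, in percentage points:

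| TXA vs control events | 253 per arm | 581 per arm |
|---|---|---|
| 0 vs 0 | −1.5 to +1.5 | −0.66 to +0.66 |
| 3 vs 0 | −0.5 to +3.4 | −0.2 to +1.5 |
| 5 vs 0 | +0.1 to +4.5 | +0.04 to +2.0 |

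These are finite where relative risk is undefined or infinite. At 5 vs 0 the interval just excludes zero while Fisher's p is above 0.05, so the interval method should be named in advance.

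**The case against.** The plan is better than its harms sentence suggests, and several replies stand.

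- **Counts are already planned.** A reader might infer that harms are summarised by relative risk alone. Section 1.11 also plans frequencies, proportions and Fisher's exact test. The accurate statement is that relative risk is the only named between-group estimate.
- **Laboratory values have their own methods.** Nothing applies relative risk to creatinine or transaminases. Section 1.11 gives continuous data summaries, t-tests and Mann-Whitney tests. All that is absent is an interval for the difference.
- **Significance is not the only safeguard.** Section 1.10 requires adverse event forms, section 3.16 gives the monitoring board the safety data, and the rule in section 3.17 is judgement-based. These govern the conduct of the trial, however, and supply no estimate for objective 2.
- **Non-significance is not near-certain for every harm.** An assumed 10% vs 20% symptom has about 87% power at 506. The point is confined to rare harms.
- **The role of the 506 analysis is unclear.** Section 1.6 ties 506 to an initial trial period, and 1,162 were planned, while section 3.16 has the board reviewing the analysis made for the report itself. The documents do not settle whether 506 is interim or final. The results at 581 per arm show that the answer does not change the conclusion.
- **Score intervals for relative risk exist.** With one empty arm such an interval has one finite limit: 0 TXA vs 3 control events of 253 gives an upper limit of about 1.27. The plan does not name this method, and 0 vs 0 remains uninformative.
- **No section says non-significance will be read as safety.** That is correct. It is a risk left open by the plan, not a stated intention. The two-day limit is already explicit in section 1.14.2.

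**Conclusion.** The point holds for rare serious harms. The plan's only harms-specific criterion has Fisher power of roughly 1% to 7% for a doubling from 0.5% or 1% at 506 women, and 9% to 21% at the full 1,162. Its only named effect estimate breaks down when an arm has no events, a 34% chance at 0.5% vs 1% and 91% at 0.1% vs 0.2% (253 per arm).

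This rests on an assumed 253/253 split, assumed harm rates and the use of Fisher's test. Completing recruitment would not cure the low power, so the defect lies in estimation and interpretation and not in the sample size.

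A reader might go further and infer that the safety analysis as a whole is uninformative, or that the trial would declare TXA safe. The documents do not support either: more common harms can be compared reasonably well, counts by arm are planned, and no such declaration is written.

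**What to change.** In section 1.11, alongside the counts and percentages already planned:

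1. For each binary adverse event, report the risk difference with a 95% interval by one named score-based or exact method (Newcombe, for example). Report relative risk only where both arms have events.
2. For outcomes with no events in an arm, report that arm's exact upper limit (0/253: 1.4% two-sided, 1.2% one-sided; 0/581: 0.63% two-sided), using the actual denominators.
3. Base the conclusion for objective 2 on these intervals and not on the significance check. State that non-significance for rare harms is not evidence of safety.
4. Optionally, add a mean difference with 95% interval to the tests planned for laboratory values.

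The cost is analysis and reporting wording only, using data already collected. The downside is a more cautious safety statement.
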